### **7.8.2 Biomarker Blood Samples**

Blood samples for ctDNA will be taken at pre-screening, if applicable, on Cycle 1 Day 1, and on Cycle 2 Day 1, Cycle 5 Day 1, and Cycle 8 Day 1, and at the EOT visit. Blood samples for ARv7 (CTC) will be collected pre-dose on Cycle 1 Day 1 and at the EOT visit. Instructions regarding sample collection, handling/processing, and shipping are provided in the Laboratory Manual.

A blood sample for ctDNA will be required at pre-screening for patients enrolling in Backfill and Expansion cohorts without AR point mutation documentation. The separate pre-screen ICF must be signed by the patient prior to collection of the pre-screening ctDNA sample (see Section [7.2](#)).

In addition to the biomarkers listed above, other biomarkers deemed relevant to gain further knowledge about the biology of the disease or about the study drug may be assayed, based on newly emerging data from the study and/or literature data. For similar reasons, unscheduled sampling may be allowed if deemed clinically relevant.

*CONFIDENTIAL*

## **8. DRUG FORMULATION, AVAILABILITY, ADMINISTRATION, AND TOXICITY INFORMATION**

### **8.1 AC176**

Investigational Product	Dosage Form and Strength	Manufacturer
AC176	Refer to the Pharmacy Manual	Accutar Biotechnology, Inc.

#### **8.1.1 Labeling, Packaging, and Supply**

AC176 will be supplied by Accutar Biotechnology, Inc. in bottles that contain 30 capsules or tablets of AC176 30 mg each. AC176 should be used only as directed by the Investigator. Store capsule bottles at 36-48°F (2-8°C) and tablet bottles between 59-77°F (15-25°C). Both capsule and tablet bottles need to be protected from light.

At the start of each cycle, patients will be dispensed sufficient supplies until the next visit. Study drug compliance will be assessed at each patient visit by review of the dosing diary. The research staff will count and document the amount of study drug taken and returned by the patient. The batch number of the study drug dispensed to the patient should be entered on the eCRF, if applicable.

The Immediate packaging will contain a statement to conform with US Food and Drug Administration (FDA) IND requirements as follows: "Caution: New Drug - Limited by federal (or United States) law to investigational use."

All study drugs must be kept in a secure place under appropriate storage conditions. Storage conditions for AC176 are included on the investigational product label.

The Sponsor or its representative must be granted access on reasonable request to check drug storage, dispensing procedures, and accountability records.

#### **8.1.2 Preparation and Administration of AC176**

AC176 is administered PO. Patients will be instructed to take one dose of AC176 at the same time immediately after a meal. For once-a-day dosing, patients will be instructed to take 1 dose of AC176 immediately after a meal in the morning and other concomitant medications in the evening; or at least 4 hours apart from taking AC176, if possible. AC176 should be taken whole with liquid(s). For BID dosing, patients will be instructed to take 1 dose of AC176 immediately after a meal in the morning and 1 dose of AC176 immediately after a meal in the evening.

The time of day for administration of AC176 should be consistent. If the patient misses a dose of study drug, the patient should take the dose as soon as possible, but not less than 12 hours (if on QD frequency) or 6 hours (if on BID frequency) before the next dose is due. If the next dose is due sooner than the above timeframe, the patient should skip the missed dose and take the next dose as scheduled.

#### **8.1.3 Precautions and Risks Associated with AC176**

Precautions and risks are located in the IB.

*CONFIDENTIAL*

Study Drug: AC176

Sponsor/Development Innovations Study Number: AC176-001/GU 207

Final Protocol: 10 July 2023 Version 4.0

## **8.2 Accountability for All Study Drugs**

The Principal Investigator (or designee) is responsible for accountability of all used and unused study drug supplies at the site.

All study drug inventories must be made available for inspection by the Sponsor or its representative, e.g., Development Innovations, and regulatory agency inspectors upon request.

Throughout the study and at its completion, Development Innovations Drug Accountability Record Forms will be completed by the site and sent to the Development Innovations Regulatory Department. Study drug supplies must not be destroyed unless prior approval has been granted by the Sponsor or its representative. Please contact the Sponsor or its representative regarding disposal of any study drug.

## **9. RESPONSE EVALUATIONS AND MEASUREMENTS**

Response and progression will be evaluated in this study using RECIST Version 1.1 and PCWG3 criteria (see [Appendix B](#) and [Appendix C](#)). Lesions are either measurable or non-measurable according to the criteria. The term “evaluable” in reference to measurability will not be used, as it does not provide additional meaning or accuracy.

Lymph nodes and bone lesions should be evaluated using PCWG3 criteria (see [Appendix B](#)) not RECIST v 1.1.

## **10. STATISTICAL CONSIDERATIONS**

### **10.1 Statistical Design**

This is a Phase I, first-in-human, open-label dose-escalation study of AC176 given as a single agent. There are two parts to this study: Part A, Dose-Escalation and Part B, Expansion cohorts. Approximately 70 patients are expected to be enrolled in the Part A Dose-Escalation cohorts, including the Backfill patients, and up to 60 patients, to the Part B Expansion cohorts. Up to 130 patients overall may enter the study.

In this study, AC176 will be given PO. The starting dose will be 30 mg. If suggested by safety or PK findings, or as appropriate based on other data from previous cohorts, then an alternative dosing schedule may be considered. However, the total daily dose would remain the same. The study will identify a MTD if possible, with safety and tolerability data (see Section [5.1.4](#)); while the totality of data collected on AC176 may be used to suggest a RP2D.

### **10.2 Sample Size Considerations**

The Phase I dose-escalation will enroll 3 patients at the 30 mg starting dose level following a standard 3+3 cohort design until the MTD, if possible, is determined in this population.

Currently, 6 dose levels are planned. The MTD will be defined based on DLTs. If 1 patient experiences a DLT at a given dose level, then that dose level will be expanded to 6 patients. Evaluation of a cohort of at least 3 patients completing 1 cycle of treatment is required prior to proceeding to the next dose level. In addition, dose level(s) which have been cleared and deemed safe may be expanded (refer to Section [5.1.2](#) Backfill cohorts).

Assuming 6 dose levels will be studied with a maximum of 6 patients enrolled per dose level, Backfilled patients may increase each cohort to a total of 12 patients, and up to approximately 70

*CONFIDENTIAL*

Study Drug: AC176

Sponsor/Development Innovations Study Number: AC176-001/GU 207

Final Protocol: 10 July 2023 Version 4.0

patients may be accrued during dose-escalation. The total number of patients enrolled to a Backfill cohort will not total more than 12 patients when combined with the number of patients previously enrolled in the same cohort. Up to 70 patients are expected to be enrolled in Part A dose-escalation cohorts, plus the backfill patients.

Depending on the totality of emerging data from safety, tolerability, PK, biomarker and preliminary anti-tumor activity, the recommended dose for expansion cohorts will be determined in Part A, dose-escalation. Two expansion cohorts may be explored in Part B expansion. The cohorts will encompass up to 30 patients with AR point mutations and 30 patients without AR point mutations. Guided by tolerability and emerging data, the Sponsor and SRC will determine the dose and schedule(s) for the expansion cohorts.

### **10.3 Analysis Population**

The following analysis populations will be used:

- Full Analysis Set (FAS)/ Safety Analysis Set (SAS) is defined as all patients who have received at least one dose of study treatment. Patients will be included in the cohort in which they have been actually treated.
- Efficacy Evaluable Set (EFF) is defined as all patients who have received any dose of study treatment and have at least one adequate post-baseline response assessment.
- PK Analysis Set includes patients who were dosed with AC176 and have any sample collection of blood with measurable concentration of AC176 in plasma.

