## GU 207 PROTOCOL SYNOPSIS

**Title of Study:** A Phase I, Open-label, Multi-center, Clinical Study to Evaluate Safety, Tolerability, Pharmacokinetics, Pharmacodynamics, and Preliminary Anti-Tumor Activity of AC176 in Patients with Metastatic Castration Resistant Prostate Cancer (mCRPC) Who Have Progressed on at Least Two Prior Systemic Therapies

**Development Innovations Study Number:** GU 207

**Sponsor:** Accutar Biotechnology, Inc.

**Phase of Study:** I

**Number of Patients:** Up to 130 patients are planned to be enrolled in this study.

Objectives:	Endpoint/Variable:
Primary Objective: Evaluate the safety and tolerability of AC176	Dose-limiting toxicities Adverse events (AEs)/Serious adverse events (SAEs) Vital signs Clinical chemistry/hematology parameters Electrocardiograms (ECGs)
Secondary Objectives: Characterize the pharmacokinetics (PK) profile of a single dose and after multiple doses of AC176	Endpoint/Variable: PK parameters
Evaluate the preliminary anti-tumor activity of AC176 on prostate specific antigen (PSA) response rate	PSA confirmed response is defined as the proportion of participants with a reduction in the level of PSA of $\geq 50\%$ from baseline to the lowest post-baseline PSA results, measured twice, at least 3 weeks apart, by the Prostate Cancer Working Group 3 criteria (PCWG3, Scher et al. 2016)
Evaluate the preliminary anti-tumor activity of AC176 on objective response rate (ORR) for patients with measurable disease	ORR based on PCWG3-modified Response Evaluation Criteria in Solid Tumors (RECIST) v1.1 (Eisenhauer et al. 2009)
Evaluate the preliminary anti-tumor activity of AC176 on duration of response (DoR)	DoR is defined as the time from the date of first documented response until date of documented progression or death in the absence of disease progression
Evaluate the preliminary anti-tumor activity of AC176 on time-to-progression (TTP)	TTP based on PCWG3-modified RECIST v1.1 and/or PCWG3 PSA criteria ( $\geq 25\%$ increase and $\geq 2$ ng/mL increase above the nadir or baseline value for patients who had a PSA decrease on treatment, which is confirmed by a second value 3 or more weeks later. For patients without a decrease on treatment, PSA progression is defined as $\geq 25\%$ increase and an absolute increase of $\geq 2$ ng/mL after 12 weeks.)

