#### **Efficacy Analysis**

All efficacy analyses will be performed using the efficacy evaluable set.

Measurement of PSA levels, bone scans and CT/MRI scans will be performed for all patients at screening, during the study according to the SOA, and at follow-up visits before a subsequent anti-cancer therapy or death.

- PSA response rate, PSA confirmed response is defined as the proportion of participants with a reduction in the PSA level of  $\geq 50\%$  from baseline to the lowest post-baseline PSA results, measured twice, at least 3 weeks apart by the PCWG3 criteria.
- Objective Response Rate (ORR), defined as the proportion of patients with confirmed complete response (CR) or partial response (PR) (i.e., 2 CRs or PRs at least 4 weeks apart) according to the PCWG3-modified RECIST Version 1.1 criteria (see [Appendix B](#)).
- Duration of Response (DoR), defined as the time from the date of first documented response (the first CR or PR which has been subsequently confirmed) until date of documented progression or death in the absence of disease progression.
- Time-to-Progression (TTP) based on PCWG3-modified RECIST v1.1 and/or PCWG3 PSA criteria ( $\geq 25\%$  increase and  $\geq 2$  ng/mL increase above the nadir or baseline value for patients who had a PSA decrease on treatment, which is confirmed by a second value 3 or more weeks later. For patients without a decrease on treatment, PSA progression is defined as  $\geq 25\%$  increase and an absolute increase of  $\geq 2$  ng/mL after 12 weeks), defined as the time from start of study treatment to disease progression.
- Radiographic Progression-Free Survival (rPFS), based on PCWG3-modified RECIST v1.1 criteria. rPFS is defined as the time from the first study drug administration to first objective

*CONFIDENTIAL*

Study Drug: AC176

Sponsor/Development Innovations Study Number: AC176-001/GU 207

Final Protocol: 10 July 2023 Version 4.0

evidence of radiographic disease progression assessed by the Study Investigator, or death, whichever occurs first.

- Progression-free Survival (PFS), based on PCWG3-modified RECIST v1.1 and/or PCWG3 PSA criteria. PFS is defined as the time from first study drug administration until objective disease progression (based on bone or CT/MRI scans), or PSA, or death, whichever occurs first.

*CONFIDENTIAL*

Study Drug: AC176  
Final Protocol: 10 July 2023 Version 4.0

Sponsor/Development Innovations Study Number: AC176-001/GU 207

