### **3. STUDY PATIENT POPULATION AND DISCONTINUATION**

#### **3.1 Inclusion Criteria**

Patients must meet the following criteria in order to be included in the research study:

1. Written informed consent, according to local guidelines, signed and dated by the patient or by a legal guardian prior to the performance of any study-specific procedures, sampling, or analyses.
2. Males who are at least 18 years-of-age at the time of signature of the informed consent form (ICF).
3. Patients with histological, pathological, or cytological confirmed diagnosis of advanced or metastatic castration resistant adenocarcinoma of the prostate excluding neuroendocrine differentiation or small cell features who have had disease progression per Prostate Cancer Working Group 3 (PCWG3) (Scher et al. 2016) guidance following standard treatment, including approved taxane-based chemotherapy, or who are not amenable (intolerability, patient choice) to standard therapies, or for whom no therapy of proven efficacy exists.
4. Progressive disease per PCWG3 guidance documented by either:
  - Positive bone scan (at least 2 new lesions) or metastatic lesions on computed tomography (CT)/magnetic resonance imaging (MRI) (Appendix B) that can be followed for response.

Or

- If PSA criteria is the only indication of progression, then the PSA values with a starting value of  $\geq 1.0$  ng/mL that have increased on at least 2 occasions obtained a minimum of 1 week apart.

5. Patients must have progressed on at least 2 prior approved systemic therapies (in any setting), with at least 1 being abiraterone, or enzalutamide, or apalutamide or darolutamide.
6. Patients must have had surgical or ongoing medical castration. Surgical castration is defined as bilateral orchiectomy. Medical castration is defined as ongoing ADT with a gonadotropin releasing hormone (GnRH) analog or inhibitor, plus serum testosterone level <50 ng/dL (or <1.7 nmol/L).
7. Eastern Cooperative Oncology Group (ECOG) Performance Status score of 0 to 1 (Appendix A).
8. Acceptable organ functions, as evidenced by the following laboratory data:
  - Renal function, as follows:
    - Creatinine clearance of  $\geq 50$  mL/min by the Cockcroft-Gault equation or equivalent
  - Liver function, as follows:
    - Total bilirubin  $\leq 1.5 \times$  ULN (unless the patient has Grade 1 bilirubin elevation due to Gilbert's disease or a similar syndrome involving slow conjugation of bilirubin)

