#### **10.4.2 Efficacy Analysis**

All efficacy analyses will be performed using the EFF.

Measurement of PSA levels, bone scans and CT/MRI scans will be performed for all patients at screening, during the study, and at follow-up visits before a subsequent anti-cancer therapy or death.

- PSA response rate, PSA confirmed response is defined as the proportion of participants with a reduction in the PSA level of  $\geq 50\%$  from baseline to the lowest post-baseline PSA results, measured twice, at least 3 weeks apart by the PCWG3 criteria.

*CONFIDENTIAL*

Study Drug: AC176

Sponsor/Development Innovations Study Number: AC176-001/GU 207

Final Protocol: 10 July 2023 Version 4.0

- Objective Response Rate (ORR), defined as the proportion of patients with confirmed complete response (CR) or partial response (PR) (i.e., 2 CRs or PRs at least 4 weeks apart) according to the PCWG3-modified RECIST Version 1.1 criteria (see [Appendix B](#)).
- Duration of Response (DoR), defined as the time from the date of first documented response (the first CR or PR which has been subsequently confirmed) until date of documented progression or death in the absence of disease progression.
- Time-to-Progression (TTP) based on PCWG3-modified RECIST v1.1 and/or PCWG3 PSA criteria ( $\geq 25\%$  increase and  $\geq 2$  ng/mL increase above the nadir or baseline value for patients who had a PSA decrease on treatment, which is confirmed by a second value 3 or more weeks later. For patients without a decrease on treatment, PSA progression is defined as  $\geq 25\%$  increase and an absolute increase of  $\geq 2$  ng/mL after 12 weeks.), defined as the time from start of study treatment to disease progression.
- Radiographic Progression-Free Survival (rPFS), based on PCWG3-modified RECIST v1.1 criteria. rPFS is defined as the time from the first study drug administration to first objective evidence of radiographic disease progression assessed by the Study Investigator, or death, whichever occurs first.
- Progression-free Survival (PFS), based on PCWG3-modified RECIST v1.1 and/or PCWG3 PSA criteria. PFS is defined as the time from first study drug administration until objective disease progression (based on bone or CT/MRI scans), or PSA, or death, whichever occurs first.

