For ORR, patients without a post-baseline tumor assessment will be classed as not evaluable (NE) and considered as non-responders, and estimates and the associated 95% CIs (based on the Clopper-Pearson method) in each dose level will be calculated.

For TTP, Kaplan-Meier curves will be generated and the median time to event, and the associated 95% CIs will be provided.

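### PFS and rPFS are analysed on a set that drops patients who die before any response assessment, and ORR is computed without the measurable-disease limit in its own objective

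*Protocol*

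**What the plan says.** Section 10.4.2 states: "All efficacy analyses will be performed using the EFF". The synopsis, under Efficacy Analysis, has the same rule: "All efficacy analyses will be performed using the efficacy evaluable set". Section 10.3 defines the EFF as "all patients who have received any dose of study treatment and have at least one adequate post-baseline response assessment". It makes no exception for death and does not say what counts as adequate. The same section defines a Full Analysis Set (FAS) of all patients with at least one dose.

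In Section 10.4.2, rPFS runs from first dose to "first objective evidence of radiographic disease progression assessed by the Study Investigator, or death, whichever occurs first". PFS adds PSA progression and also ends at death.

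For ORR, the synopsis and Table 3 in Section 2 state the objective as "objective response rate (ORR) for patients with measurable disease". Section 10.4.2 defines ORR only as a share of patients with confirmed CR or PR and does not mention measurable disease. It then adds that "patients without a post-baseline tumor assessment will be classed as not evaluable (NE) and considered as non-responders".

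Section 3.1 does not ask for measurable disease. Criterion 4 can be met by a bone scan, or by PSA alone (the bullet that begins "If PSA criteria is the only indication of progression").

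**The concern.** **PFS and rPFS.** Membership of the EFF depends on living long enough to be assessed, and death is part of the endpoint. A death before the first assessment is an event by definition, but the patient is not in the set. Each such death removes an early event and raises the curve. The bias comes from early deaths only:

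- Patients who stop early without progression normally get imaging at end of treatment (Section 7.5.1) and a PSA (Table 2, footnote m), so they enter the EFF.
- TTP does not count death and is not affected by this route.

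**ORR.** Under Table 7 in Appendix B, a patient with no soft-tissue lesions at baseline can be rated only Non-PD or PD. As Section 10.4.2 is written, he is in the denominator and cannot be a responder. The objective and the analysis describe two different quantities.

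The two errors act in opposite directions, and nothing holds either share constant across dose levels or between the two expansion cohorts. Preliminary anti-tumor activity is among the data that inform the expansion dose (Section 10.2).

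**Working it through.** The protocol states no target, power or expected value for PFS, rPFS or ORR, so there is no figure to reproduce. The following sizes the effect under stated assumptions.

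**Inputs from the protocol**
- About 30 patients per expansion cohort; up to 12 per dose level with backfill (Section 10.2).
- First post-baseline PSA at Cycle 2 Day 1, about week 4; first scan at week 8, for 28-day cycles (Section 7.4.1, Table 2).
- Clopper-Pearson 95% intervals for ORR (Section 10.4.2).

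**Assumed, not in the protocol**
- Exponential PFS with a true median of 4 months in all treated patients.
- A share q who die before any assessment.
- The share of patients with measurable disease, and the response rate among them.

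**PFS and rPFS, from truth to EFF.** Once the assessment window has passed, dropping early deaths gives S_EFF(t) = S(t)/(1 − q). The EFF median therefore solves S(t) = 0.5(1 − q), which gives

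median_EFF = 4 × (1 − log2(1 − q)).

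For q = 1/30: log2(29/30) = −0.0489, so 4 × 1.0489 = 4.20 months. True 6-month PFS is 2^(−6/4) = 35.4%.

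| q | EFF median (months) | EFF 6-month PFS |
|---|---|---|
| 3% | 4.18 | 36.4% |
| 5% | 4.30 | 37.2% |
| 10% | 4.61 | 39.3% |

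In counts, 1, 2 or 3 such deaths in 30 patients give 4.20, 4.40 or 4.61 months. One in a dose level of 12 gives 4.50. A simulation of 2,000,000 patients with only early deaths removed gave medians of 4.17, 4.29 and 4.60 months for q = 3%, 5% and 10%, and the same 6-month values.

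**PFS and rPFS, from EFF back to all treated.** Suppose instead that the EFF median is 4.0 months and k of 30 patients died before assessment. Then S_FAS(t) = ((30 − k)/30) × S_EFF(t). With an exponential tail after the first assessment at t0, the rate is ln 2/(4 − t0) and

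median_FAS = t0 + ln(2 × (30 − k)/30) × (4 − t0)/ln 2.

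| k of 30 | All-treated curve where EFF reads 50% | Median, t0 = week 4 (months) | Median, t0 = week 8 (months) |
|---|---|---|---|
| 1 | 48.3% | 3.85 | 3.89 |
| 2 | 46.7% | 3.69 | 3.78 |
| 3 | 45.0% | 3.53 | 3.67 |
| 5 | 41.7% | 3.19 | 3.43 |

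**ORR.** If patients without measurable disease do not respond, reported ORR = (ORR in measurable disease) × (measurable share). A true 40% is reported as 0.40 × 0.30 = 12%, 0.40 × 0.50 = 20% or 0.40 × 0.70 = 28%. In counts for a cohort of 30:

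| Measurable-disease ORR (95% CI) | Reported over all 30 (95% CI) |
|---|---|
| 6/15 = 40.0% (16.3–67.7) | 6/30 = 20.0% (7.7–38.6) |
| 4/12 = 33.3% (9.9–65.1) | 4/30 = 13.3% (3.8–30.7) |
| 6/18 = 33.3% (13.3–59.0) | 6/30 = 20.0% (7.7–38.6) |
| 8/24 = 33.3% (15.6–55.3) | 8/30 = 26.7% (12.3–45.9) |

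The no-response assumption is slightly too strict. Table 7 would allow a CR in a patient who has only non-target soft-tissue lesions and no bone lesions.

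**The non-responder rule.** Section 10.4.2 counts patients without a post-baseline tumor assessment as non-responders. The EFF has already removed anyone with no response assessment at all, so the rule can act only on patients who enter the EFF through PSA alone. With 6 responders among 30 treated, dropping 1 to 5 unassessed patients moves ORR from 20.0% to 6/29 = 20.7% up to 6/25 = 24.0%.

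**The case against.** The strongest reply is about size and about what belongs in an SAP.

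- **The PFS effect is probably small.** Entry requires ECOG 0–1 and a life expectancy of at least 3 months (Section 3.1). At q = 3% the median moves by about 5 days. With 30 events, an exponential 95% interval around a 4-month median is 4 × exp(±1.96/√30), about 2.8 to 5.7 months. This stands as a limit on size. It does not remove the bias, which always has the same sign and costs nothing to avoid.
- **The window is unclear.** If a PSA value is an adequate assessment, only deaths before about week 4 are lost; if only imaging counts, the window is about 8 weeks (3 and 6 weeks in 21-day cycles). This also stands, but patients are excluded under either reading.
- **The ORR restriction is already in the objective.** An SAP could carry it into the denominator. But Section 10.4.2 names the set for all efficacy analyses and defines ORR itself. An SAP that followed it to the letter would give the diluted figure.
- **Progression by PSA alone does not mean that measurable lesions are absent.** Correct. Criterion 4 describes how progression was documented. It shows that measurable disease is not required, not how many patients lack it.
- **No formal comparison is planned.** True: the endpoints are secondary and reported descriptively. The point is about reading those estimates, not about a test.

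One further assumption should be plain. Withdrawals without any assessment are taken to be censored near day 1 and so to matter little; the protocol gives no censoring rules.

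**Conclusion.** Both parts hold on the protocol's text. PFS and rPFS on the EFF are biased upward whenever a treated patient dies before an adequate assessment. Under an assumed 4-month median, the EFF median is 4.2 to 4.6 months for 1 to 3 such deaths in 30, and the entry criteria point to the low end. ORR as written in Section 10.4.2 does not match its objective. The dilution can be large: an assumed 40% reads as 12% to 28% when 30% to 70% of patients have measurable disease. The direction of each effect follows from the definitions, but the sizes rest on shares that the protocol does not give. The PFS and rPFS point is enough by itself to justify a change. The matter should be fixed but is not critical, because the primary safety analysis already uses all treated patients.

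**What to change.** Change Section 10.4.2 and the synopsis efficacy text as follows:

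1. Analyse PFS and rPFS on the FAS, which Section 10.3 already defines, with death as an event.
2. Compute ORR on treated patients with measurable disease at baseline, and count those without a post-baseline tumor assessment as non-responders, as Section 10.4.2 already intends.
3. Keep the EFF for supportive analyses, and say in Section 10.3 whether a PSA value alone is an adequate response assessment.

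Moving TTP and PSA response to the FAS is optional.

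The cost is wording only, with no new data or patients. PFS and rPFS may look slightly less favourable, and ORR will have a smaller denominator and a wider interval.
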